2. BACKGROUND AND RATIONALE

2.1 Problem Statement

Sleep disturbances are highly prevalent among pregnant women, particularly in the third trimester. Poor sleep quality can lead to adverse maternal and fetal outcomes, including increased risk of preeclampsia, prolonged labor, and depressive symptoms. While pharmacological interventions are often avoided during pregnancy due to safety concerns, non-pharmacological interventions such as physical activity are recommended.

2.2 Rationale

Physical activity is known to improve sleep quality in the general population. However, comparative data regarding specific types of exercise—specifically Traditional Pregnancy Exercise (Senam Hamil) versus Stretching Exercises—is limited. Understanding which modality is more effective for improving sleep quality (assessed via PSQI) will help healthcare providers prescribe the most appropriate activity for third-trimester mothers.

2.3 Research Hypothesis

1. There is a significant difference in sleep quality scores between pregnant women performing traditional pregnancy exercises and those performing stretching exercises.
2. Both exercise modalities will result in improved sleep quality scores compared to baseline.

3. STUDY OBJECTIVES

3.1 Primary Objective

To compare the effectiveness of Traditional Pregnancy Exercise versus Stretching Exercise on sleep quality scores in third-trimester pregnant women.

3.2 Secondary Objectives

- To assess the change in anxiety levels (HARS scores) associated with both exercise interventions.
- To evaluate physiological responses (blood pressure/diastolic measures) pre- and post-intervention.

4. STUDY DESIGN

4.1 Study Type

- **Type:** Interventional (Clinical Trial)
- **Design:** Quasi-Experimental (Non-randomized trial)
- **Allocation:** Non-randomized Parallel Assignment (Two Arms)
- **Masking:** Open Label (Participants and instructors know the intervention; Outcome assessors should ideally be blinded if possible).

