7. OUTCOME MEASURES

7.1 Primary Outcome

- **Measure:** Sleep Quality.
- **Instrument:** Pittsburgh Sleep Quality Index (PSQI) - Indonesian validated version.
- **Time Frame:** Baseline (Pre-test) and Post-intervention (Post-test, after [X] weeks).
- **Metric:** Total PSQI score (Range 0-21; lower scores indicate better sleep quality).

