7.3 Confounding Variables

- Age, Parity, BMI, Gestational Age.

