8.2 Statistical Methods

- **Descriptive Statistics:** Means/Standard Deviations for continuous variables; Frequencies/Percentages for categorical variables.
- **Baseline Comparability:** Independent t-tests or Chi-square tests to ensure groups are balanced at baseline (specifically checking HARS and Diastolic BP as noted in preliminary analysis).
- **Outcome Analysis:** A **Linear Mixed Model** is used to analyze the difference between groups while adjusting for baseline scores and confounding variables (e.g., Age, Parity).
- **Significance Level:** p-value < 0.05.

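### Allocation to the two exercise arms is non-random, with no stated rule or reason, so the PSQI comparison is open to confounding that the planned model can reduce but not fully remove.

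*Combined protocol and SAP*

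**What the plan says.** Section 4.1 labels the trial "Quasi-Experimental (Non-randomized trial" and gives the allocation as "Non-randomized Parallel Assignment (Two Arms". On masking it says "Participants and instructors know the intervention; Outcome assessors should ideally be blinded if possible". The primary objective in 3.1 is "To compare the effectiveness of Traditional Pregnancy Exercise versus Stretching Exercise on sleep quality scores", and 2.2 says the answer will help providers choose which programme to prescribe. The primary metric in 7.1 is "Total PSQI score (Range 0-21; lower scores indicate better sleep quality".

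Section 8.2 offers two protections. Baseline t-tests or chi-square tests are to be run "to ensure groups are balanced at baseline", with HARS and diastolic blood pressure singled out. A linear mixed model then compares the groups while "adjusting for baseline scores and confounding variables (e.g., Age, Parity". Section 7.3 lists four confounders: "Age, Parity, BMI, Gestational Age".

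The available text does not say who places a woman in Group A or Group B, by what rule (her choice, clinic, class, calendar order), or why randomisation is not used. It plans no matching, propensity method or sensitivity analysis for unmeasured confounding, and it acknowledges no limitation on causal reading.

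**The concern.** The objective asks which programme works better, and that is a causal contrast. Without randomisation, a difference in PSQI between arms mixes the effect of the programme with the effect of who ended up in it. Women who choose or are steered to one programme may differ in motivation, previous exercise, employment or support at home, and none of these is listed as a covariate. If arms are formed by clinic or class, arm and site coincide and no covariate can separate them.

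Confounding bias does not shrink as the sample grows. To the extent that it survives adjustment, a p-value below 0.05 no longer corresponds to a 5% error rate. Without the allocation rule, a reader cannot judge how large the problem is likely to be.

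**Working it through.** **Inputs from section 5.1.** The group SDs are 2.86 (n = 39) and 3.12 (n = 38), the planned difference is 6.84 − 10.10 = −3.26 points, and there are 30 women per arm. The significance level is 0.05, with the two-sided z of 1.96.

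**Plan's own figure.** Pooled S = √[(2.86² × 38 + 3.12² × 37)/75] = √(670.9976/75) = 2.991, which reproduces. The 30 per arm is taken as planned; how it was derived is a separate matter.

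**Can baseline tests secure balance?** SE of a difference in means = 2.991 × √(2/30) = 0.772. The significance boundary is t(0.975, 58 df) × SE = 2.0017 × 0.772 = 1.546 points. A true baseline imbalance of half an SD (2.991/2 = 1.50 points, if the baseline SD is also 2.99) lies below that boundary, and the t-test detects it only 48% of the time. Factors that are not measured are not tested at all.

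**Effect of a confounder, unadjusted test.** Assumption, not from the documents: an unmeasured factor worth 3 PSQI points whose prevalence differs between arms. Bias = 3 × prevalence gap. With no true effect, the rejection rate comes from the non-central t with 58 df and non-centrality bias/SE.

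| Prevalence gap | Bias (points) | Share of 3.26 | Bias/SE | False-positive rate |
|---|---|---|---|---|
| 0 | 0 | 0% | 0 | 5% |
| 10 points | 0.3 | 9% | 0.39 | 6.7% |
| 20 points | 0.6 | 18% | 0.78 | 11.9% |
| 30 points | 0.9 | 28% | 1.17 | 20.9% |
| 40 points | 1.2 | 37% | 1.55 | 33.3% |

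**Same confounder, adjusted for baseline PSQI.** Suppose the factor shifts PSQI equally at both visits, the pre-post correlation is r (not given in the documents), and the baseline slope is r. Adjustment then multiplies the bias by (1 − r) and the SE by √(1 − r²). For example, at r = 0.5 and a 40-point gap, bias = 1.2 × 0.5 = 0.6, SE = 0.772 × 0.866 = 0.669, and the ratio is 0.90.

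| r | 10-point gap | 20-point gap | 40-point gap |
|---|---|---|---|
| 0.3 | 5.9% | 9% | 20% |
| 0.5 | 5.6% | 7% | 14% |
| 0.7 | 5.3% | 6% | 10% |

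**Confounder unrelated to baseline PSQI.** If the factor acts only on change in sleep, baseline adjustment leaves the bias intact and narrows the SE. At r = 0.5, biases of 0.6 and 1.2 then give about 14% and 42%. This is the case that the planned model does not protect against.

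**Covariates.** Section 8.2 names age and parity only as examples. Section 7.3 adds BMI and gestational age. HARS and diastolic blood pressure are singled out for balance checks but are not among the confounders in 7.3. The adjustment set is therefore not fixed in advance.

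**The case against.** The design is openly declared as quasi-experimental, so there is no internal contradiction. Much of the objection to a harsher criticism stands.

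- A reader might infer that the planned adjustment does nothing about selection bias. It does something. Baseline PSQI, age, parity, BMI and gestational age are all measured, and a stable tendency to sleep badly shows up in baseline PSQI and is partly removed.
- A reader might take 12% to 33% as the error rate of the planned analysis. Those figures belong to an unadjusted test, which is not the planned one. The assumed factor is also large: 3 points is 92% of the planned difference (3/3.26) and about one SD.
- A reader might infer that nothing stands in the way of randomising. The documents are silent, which is weaker. One catchment area in 5.2 need not mean one clinic. Section 6.2 speaks of a traditional class, whereas most stretches in Figure S2 are carried out manually by a therapist, so feasibility could differ between sites. All that can be said is that no reason is given.
- Randomisation may come too late. Section 4.2 plans August to October 2025, and 8.2 mentions a preliminary analysis. The documents do not settle whether women have already been allocated.

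What remains is that declaring the design neither supplies the allocation rule nor removes unmeasured confounding, and the objective is still worded as comparative effectiveness.

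**Conclusion.** The point holds as a design weakness with a missing allocation rule and rationale. As written, the primary PSQI contrast cannot carry the causal reading that 3.1 gives it. The planned model reduces confounding from measured variables but not from unmeasured factors that affect change in sleep, and the baseline tests cannot secure balance.

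The size is illustrative only. It rests on an assumed 3-point factor, an assumed prevalence gap and an assumed pre-post correlation. For a 20- to 40-point gap, the false-positive rate is about 12% to 33% unadjusted. For a factor acting equally at both visits it is about 9% to 20%, 7% to 14% or 6% to 10% after baseline adjustment, at correlations of 0.3, 0.5 and 0.7. A 10-point gap gives about 5% to 7%, adjusted or not. The documents do not show that bias of any particular size will occur.

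**What to change.** **If enrolment has not begun:** in 4.1, replace non-randomised allocation with individual 1:1 randomisation from a computer-generated permuted-block list, concealed until after consent and the baseline PSQI. Keep the adjusted model in 8.2.

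**If women have already been allocated:** state in 4.1 the rule actually used and the reason for it. In 8.2, fix the covariates as baseline PSQI plus all four confounders in 7.3. Word 3.1 and the conclusion as an adjusted association, not as comparative effectiveness.

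**Cost:** the first route needs a protocol amendment and a concealed list, with the same 60 women and the same visits. Women could not choose their programme, so a few may decline, and both programmes must be available wherever women are recruited. The second route costs only text, but it limits what the trial can claim.

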4.2 Study Timeline

- **Estimated Start Date:** 4th August 2025
- **Estimated Completion Date:** 4th October 2025
- **Intervention Duration:** 3 weeks per participant, 45-60 minutes per session.

5. STUDY POPULATION

5.1 Sample Size

Total sample size: N = 60

- Intervention Group: n = 30
- Control (Comparator) Group: n = 30

$$n = 2 \left[\frac{\left(Z_{1-\frac{\alpha}{2}} + Z_{1-\beta} \right) S}{X_1 - X_2} \right]^2$$
$$n = 2 \left[\frac{(1,96 + 0,84)2,9910925540121}{6,84 - 10,10} \right]^2$$
$$n = 2 \left[\frac{(2,8)2,9910925540121}{-3,26} \right]^2$$

$$n = 2 \left[\frac{8,3750591512338}{-3,26} \right]^2$$

$$n = 2[-2,569036549458]^2$$

$$n = [-5,138073098916]^2$$

$$n = [26,399795169806]$$

$$n = 26,399795169806 \text{ adding } 10\%.$$

Therefore, a minimum of 30 respondents per group is required

S value is calculated in the following:

$$S = \sqrt{\frac{S_1^2(n_1 - 1) + S_2^2(n_2 - 1)}{n_1 + n_2 - 2}}$$

$$S = \sqrt{\frac{2,86^2 (39 - 1) + 3,12^2 (38 - 1)}{39 + 38 - 2}}$$

$$S = \sqrt{\frac{2,86^2 (39 - 1) + 3,12^2 (38 - 1)}{39 + 38 - 2}}$$

$$S = \sqrt{\frac{8,1796(38) + 9,7344(37)}{75}}$$

$$S = \sqrt{\frac{310,8248 + 360,1728}{75}}$$

$$S = \sqrt{\frac{670,9976}{75}}$$

$$S = \sqrt{\frac{670,9976}{75}}$$

$$S = \sqrt{8,9466346666}$$

$$S = 2,9910925540121$$

Notes :

n : Sample size
 Z : Z-score
 $Z_{1-\alpha/2}$: 1.96 at the 95% confidence interval
 $Z_{1-\beta}$: Statistical power at 0.84
 S : Standar deviasi gabungan
 $X_1 - X_2$: The minimum significant mean difference observed in prior research (6,84) ($6,84 - 10,10 = -3,26$) (Blanquea,dkk. 2018)
 S : Weighted average of standard deviations from two groups (2,99)
 S_1 : Standard deviation in group 1 (2,86) (Blanquea,dkk. 2018)
 n_1 : Sampel size in group 1 (39)
 S_2 : Standard deviation in group 2 (3,12) (Blanquea,dkk. 2018)
 n_2 : Sampel size in group 2 (38)

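### The sample-size working squares the leading factor 2, so 26.4 (then 30) per group is double what the plan's own formula gives; 30 per group has about 98.6% power for 3.26 points, not the implied 80%

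*Combined protocol and SAP*

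**What the plan says.** Section 5.1 gives n = 2[(Z(1−α/2) + Z(1−β)) S / (X1 − X2)]² and uses the result as a number per group. The inputs are:

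- a two-sided alpha of 0.05, entered as z ("1.96 at the 95% confidence interval");
- a second z-value of 0.84, described in the notes as "Statistical power at 0.84";
- a mean difference of 6.84 − 10.10 = −3.26 PSQI points from a cited study;
- a pooled SD from that study, "S = 2,9910925540121".

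The working reaches "n = 2[-2,569036549458]^2", continues with "n = [-5,138073098916]^2", and arrives at 26.399795169806. It then adds 10% and concludes: "Therefore, a minimum of 30 respondents per group is required". The planned enrolment is 30 + 30 = 60.

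**The concern.** The formula squares only the bracket. Between the two quoted lines the 2 is multiplied into the bracket and then squared with it, so the multiplier becomes 4 and every later figure is doubled.

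This calculation is the plan's only justification for enrolling 60 women, and the minimum it claims does not follow from its inputs. It also misinforms whoever interprets the result. A reader who accepts section 5.1 will believe that the trial has 80% power at 3.26 points and less for anything smaller. On the plan's assumptions it has 80% power for a clearly smaller difference, so a null result would say more than section 5.1 suggests.

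The label on 0.84 adds to the confusion. The intended power of 80% is written nowhere, and a literal reader would take it to be 84%.

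**Working it through.** All inputs are from section 5.1, with decimal commas written as points.

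**1. Pooled SD.** S = √[(2.86² × 38 + 3.12² × 37) / 75] = √[(310.8248 + 360.1728) / 75] = √8.94663 = 2.99109. This matches the plan.

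**2. Ratio inside the bracket.** k = (1.96 + 0.84) × 2.99109 / 3.26 = 8.37506 / 3.26 = 2.569037. This matches the plan apart from the sign, which the square removes.

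**3. The plan's figure.** (2k)² = 5.138073² = 26.3998. This is the plan's result, and it arises only when the 2 is squared.

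**4. The stated formula.** 2k² = 2 × 6.59995 = 13.20, so 14 per group. The ratio 26.40 / 13.20 is exactly 2.

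**5. The 10% step.**

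- Plan: 26.40 × 1.1 = 29.04, or 26.40 / 0.9 = 29.33. Both round up to 30, so this step is sound and the whole discrepancy comes from step 3.
- Corrected: 13.20 × 1.1 = 14.52, or 13.20 / 0.9 = 14.67. Both round up to 15. Rounding to 14 first gives 14 × 1.1 = 15.4, so 16.

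**6. Other readings of the inputs.** Per-group numbers before inflation:

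| Reading | n per group |
|---|---|
| One-sided alpha, 80% power | 11 |
| Two-sided, 80% power, t-test instead of z | 14.24, so 15 |
| Two-sided, 0.84 taken as 84% power | about 15 |
| Two-sided, 90% power | 18 |
| Two-sided, 95% power | 22 |

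None gives 26.4.

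**7. The label.** Φ(0.84) = 0.7995, so 0.84 is the z-value for 80% power.

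**8. What 30 per group provides.** By the normal approximation, power = Φ(3.26 / [S√(2/n)] − 1.96), and the difference detectable with 80% power is 2.80 × S√(2/n).

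- n = 30: S√(2/30) = 0.7723. Power = Φ(4.221 − 1.96) = Φ(2.261) = 98.8%. Detectable difference = 2.80 × 0.7723 = 2.16.
- n = 27 (30 × 0.9, if the 10% is an allowance for loss): S√(2/27) = 0.8141. Power = Φ(4.005 − 1.96) = Φ(2.045) = 98.0%. Detectable difference = 2.80 × 0.8141 = 2.28.

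The two-sample t-test (noncentral t) gives slightly lower power:

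| n per group | Power for 3.26 points | Difference detectable with 80% power |
|---|---|---|
| 14 | 79.3% | – |
| 15 | 82.2% | – |
| 27 | 97.6% | 2.32 |
| 30 | 98.6% | 2.20 |

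**The case against.** The strongest objection is that the error is harmless in direction. It enlarges the trial, leaves power for 3.26 points well above the implied 80%, and alters no endpoint, analysis or allocation. That is true, and it is why enrolment need not change. It does not rescue the section, because the stated minimum is still wrong and so is the detectable difference a reader would infer.

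A second defence is that 26.40 is a correct figure for both groups together (2 × 13.20). The plan does not use it that way: it carries 26.40 forward as a per-group number and doubles it again to reach 60.

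Three cautions stand and affect how the correction is worded:

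- The power figures are for an unadjusted comparison of two means, as in the plan's own formula. Section 8.2 plans a linear mixed model adjusted for baseline and confounders, and section 4.1 makes the design non-randomised. Baseline adjustment may raise precision, and covariates associated with group may lower it. The plan gives no correlations from which to judge either.
- Section 5.1 adds 10% without giving a reason. Reading it as loss to follow-up, and hence 27 per group, is conventional but is an assumption.
- The label on 0.84 is an editorial fault. No number depends on it.

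**Conclusion.** The concern holds. On the plan's inputs the formula gives 13.20 per group, not 26.40, which means 14 per group before inflation and 15 to 16 after, against the stated 30. The doubling is exact for the unrounded result; for the inflated figure it depends on when one rounds.

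The trial is larger than its formula requires. With 30 per group, power for 3.26 points is about 98.6%, and 80% power is reached at about 2.2 points. With 27 per group the figures are 97.6% and about 2.3 points.

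These results take as given the SD of 2.99 and the difference of 3.26 from the cited study, two-sided alpha 0.05, equal groups and an unadjusted two-sample t-test. Whether 3.26 points is realistic between two exercise programmes is a separate question that this check does not address.

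**What to change.** In section 5.1:

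1. Replace the faulty line and those after it with n = 2 × 6.600 = 13.20, so 14 per group by this formula, or 15 to 16 with 10% added.
2. Keep 30 per group and replace the claim that it is the required minimum with what it provides. Suggested text:

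> Thirty women per group (27 if 10% are lost) give about 98% power for a difference of 3.26 PSQI points, or 80% power for about 2.2 to 2.3 points, by an unadjusted two-sample t-test with two-sided alpha 0.05 and SD 2.99.

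3. State what the 10% allowance is for.
4. Change the note on Z(1−β) to say that z = 0.84 corresponds to 80% power.

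The cost is rewording section 5.1. Enrolment, procedures and analysis stay as they are.

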5.2 Inclusion Criteria

1. Pregnant women in the third trimester (Gestational age 28–40 weeks).
2. Singleton pregnancy.
3. Willing to participate and sign informed consent.
4. Able to perform moderate physical activity.
5. Based in the study catchment area (Palangka Raya).

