8. STATISTICAL ANALYSIS PLAN

8.1 Data Management

Data is collected via paper questionnaires and entered into a digital database (SPSS). Data cleaning is performed to check for outliers and missing values.

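### The 28–40 week eligibility window is not tied to the 3-week programme, and no rule covers women who deliver before the only post-baseline PSQI

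*Combined protocol and SAP*

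**What the plan says.** - **Eligibility (5.2):** "Pregnant women in the third trimester (Gestational age 28–40 weeks". The time at which gestational age is assessed is not stated.
- **Programme length (4.2):** "3 weeks per participant, 45-60 minutes per session". The same section puts estimated completion at "4th October 2025", from a start on 4 August 2025.
- **Primary outcome (7.1):** PSQI at "Baseline (Pre-test) and Post-intervention (Post-test, after [X] weeks". There is one post-baseline measurement, and its week is an unfilled placeholder.
- **Objective (3.1):** the effect is sought "on sleep quality scores in third-trimester pregnant women".
- **Allocation (4.1):** "Non-randomized Parallel Assignment (Two Arms".
- **Confounders (7.3):** "Age, Parity, BMI, Gestational Age". Section 8.2 adjusts the mixed model for baseline score and confounders, naming only age and parity, as examples.
- **Missing data (8.1):** "Data cleaning is performed to check for outliers and missing values". No handling rule follows.

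The exclusions (5.3), adherence monitoring (6.3), statistical methods (8.2) and safety monitoring (9.3) do not mention delivery during the programme. Section 9.3 covers stopping the exercise for complications. It does not say what happens to the post-test.

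**The concern.** The primary outcome is sleep in late pregnancy. Once a woman has delivered, that outcome no longer exists for her, so this is not ordinary missing data. A PSQI taken after birth measures something else. The plan does not say whether such a score would be collected, used or discarded, so in an open-label trial the choice could be made after the data are seen. If the score is not collected, a mixed model with baseline as a covariate and one post-test recovers little for that woman.

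Whether a woman is affected depends strongly on her gestational age at entry. The arms are not randomised, so they need not share the same entry distribution. The number of women affected, and the mixture of pregnancy and postpartum scores, could therefore differ between arms for reasons unrelated to the exercise.

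**Working it through.** The plan gives no figure for deliveries before the post-test, so there is none to reproduce. Section 5.1 adds 10% to the sample size without stating why.

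**1. Timing, from the documents alone.** The 3-week interval is inferred from 4.2 together with the post-intervention label in 7.1, because 7.1 leaves the week blank. Post-test week = entry week + 3. The latest entry that keeps the post-test within the plan's own window is 40 − 3 = 37 weeks.

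**2. Chance of delivering first, by week of entry.** Assumption, not in the documents: delivery is normal with mean 39.0–39.8 weeks and SD 1.3–1.5. With F its distribution function, for a woman still pregnant at entry week g:

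P(g) = [F(g+3) − F(g)] / [1 − F(g)]

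Example, mean 39.0, SD 1.5, g = 37: F(40) = 0.7475 and F(37) = 0.0912, so P = (0.7475 − 0.0912)/0.9088 = 0.722.

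| Entry week | 39.0/1.5 | 39.4/1.5 | 39.5/1.3 | 39.8/1.3 |
|---|---|---|---|---|
| 35 | .250 | .174 | .124 | .083 |
| 36 | .488 | .388 | .348 | .268 |
| 37 | .722 | .635 | .640 | .554 |
| 38 | .878 | .827 | .858 | .806 |

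**3. Overall share, using the dates in 4.2.** 4 August to 4 October is 27 + 30 + 4 = 61 days. If completion includes the last post-test, 61 − 21 = 40 days (5.71 weeks) remain for entry. Two entry patterns fit this:

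- A: women are drawn at a constant rate from those then pregnant at 28–40 weeks. Share = ∫[F(g+3) − F(g)]dg / ∫[1 − F(g)]dg over 28–40.
- B: all eligible women are enrolled at the start, then only women reaching 28 weeks. This adds 5.71 to the denominator and almost nothing to the numerator.

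For mean 39.0, SD 1.5: A = 2.775/10.773 = .258; B = 2.775/(10.773 + 5.714) = .168.

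| Quantity | 39.0/1.5 | 39.4/1.5 | 39.5/1.3 | 39.8/1.3 |
|---|---|---|---|---|
| A: deliver first | .258 | .240 | .241 | .227 |
| B: deliver first | .168 | .159 | .159 | .151 |
| A: enter past 37 weeks | .171 | .189 | .197 | .209 |
| B: enter past 37 weeks | .111 | .125 | .131 | .139 |
| Uniform entry 28–37: deliver first | .133 | .103 | .089 | .069 |

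Of 60 women, 15–26% is about 9 to 16, and 7–13% is about 4 to 8.

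**4. Power.** Inputs from 5.1: difference 3.26; pooled SD √(670.9976/75) = 2.991, which reproduces. At 25% loss, 30 × 0.75 = 22.5 per group. A two-sided 5% t-test has power .942 with 22 per group and .951 with 23. The per-group figure of 26.4 in 5.1 is not used here.

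**The case against.** **The window may describe the whole study period.** The eligibility line can be taken as a definition of the third trimester that holds throughout, which would imply entry by 37 weeks. A reader might infer that the plan certainly enrols women at 40 weeks and tests them at 43. That holds only if the window applies at entry and is used to its limit. Entry is the plain reading of an inclusion criterion, but the text does not settle it. The missing delivery rule survives both readings.

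**The blank interval is a template gap.** Section 6.1 has similar unfilled placeholders. This is fair, and three weeks remains an inference, though a reasonable one.

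**The size is assumption-driven.** This stands. If entry is assumed to be concentrated near 40 weeks, shares of 39–53% can be produced, with power of about 79% at 53% loss. Nothing in the documents supports that entry pattern.

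**Bias in the arm comparison may be small.** A reader might infer a spurious arm difference approaching one PSQI point. Getting there needs two stacked assumptions: arms entering over 28–38 and 30–40 weeks, and a postpartum worsening of 2–5 points. Together they give about 0.3–0.9 points unadjusted. The documents support neither. Gestational age is already listed in 7.3; with it as a linear covariate, the same illustration gives −0.15 to +0.03. Nor do the documents say that postpartum scores would be used. They leave the question open.

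**Analysing only women still pregnant is itself a selection.** This is correct. It conditions on an event after baseline, and the assumption it needs has to be stated.

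**Conclusion.** The point holds as an omission with a definite consequence. The eligibility window is not matched to the programme length, and the plan does not say how delivery before the only post-baseline PSQI is treated. If the window applies at entry, it admits women who mostly cannot supply the outcome named in the objective: at 38 weeks, 81–88% would deliver first under the stated assumptions.

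Confidence in the gap is high and in its size is limited. The ranges of 15–26% and 7–13% rest on an assumed delivery distribution, the 3-week interval and the entry patterns described. The main harm is to what the primary comparison means. Arm comparability is also at risk if gestational age at entry differs between arms, although adjusting for it should remove most of the average imbalance. Adjustment does not turn a postpartum score into a third-trimester one. Power is not the issue: about 94–95% remains at 25% loss for the assumed 3.26-point difference. The plan should be corrected, but the gap does not by itself undermine the trial.

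**What to change.** 1. **Section 5.2.** State that gestational age is assessed at enrolment and reconcile its upper limit with the 3-week programme. The value 37 is only an arithmetic bound: 55–72% of women entering exactly then would still deliver first under the assumptions above. The sponsor should set the limit from a stated tolerance for delivery before the post-test.
2. **Section 7.1.** Fill the blank interval consistently with section 4.2. Require the primary PSQI to be completed before delivery, and exclude postpartum scores from the primary outcome.
3. **Section 8.2.** Name baseline gestational age as a covariate. Define delivery before the post-test as an intercurrent event, impute no pregnancy score after it, and report the number by arm. State that comparing women still pregnant at the post-test assumes delivery timing is unaffected by arm and unrelated to sleep, given baseline gestational age and the other covariates.
4. **Sensitivity analysis.** Whether or not enrolment can still change, repeat the primary analysis in women who entered early enough that delivery before the post-test is unlikely. The selection assumption matters least there.

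The edits amount to one eligibility line, one outcome line and a short analysis paragraph. The real cost is a smaller recruitment pool in a short entry window, since about 11–21% of entrants would be past 37 weeks under patterns A and B, and no inference for women entering after the limit.
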